5.3 Methods of Pooling Data

Clinical sites follow a common protocol, are monitored for compliance with the protocol, and report data collected via a central electronic database. These factors allow the data to be pooled and analyzed jointly across sites (Meinert, 1986).

5.4 Withdrawals and Loss to Follow-up

Subjects have the right to withdraw participation in the study at any time and for any reason or for no reason and will be removed from the study upon request. At the time of withdrawal from the study, if possible, an EoS visit should be conducted to complete all assessments scheduled for a safety follow-up visit in either study part as shown in the schedule of assessments. Subjects who withdraw prematurely from the study for any reason will not be eligible to participate in the OLE study. Details regarding subjects who choose to discontinue study participation will be recorded on the appropriate page(s) of the eCRF.

A subject will be considered lost to follow-up if he/she repeatedly fails to return for scheduled visits and is unable to be contacted by the study site.

5.5 Analysis Visit Windows

5.5.1 Windowing of the AOBP and the Laboratory Measurements

All efficacy analyses of the AOBP and laboratory measurements will use analysis visits assigned by study day ranges relative to DB treatment start or TP2 first dose (TP2 visits only). Scheduled, unscheduled, EoT, or EoS/early withdrawal (EW) efficacy assessments will be mapped to an analysis visit. In cases where a subject has multiple assessments windowed to the same analysis visit, the assessment closest to the protocol-specific target day will be selected for analysis. Screening will not be windowed; nominal visits will be used. In the case of multiple screening visits, the visit closest to the start of the Run-in Period Visit will be used. Visits during the safety follow-up period will not be windowed.

The Study Baseline is the measurement with the datetime of the measurement that is closest to the before the datetime of first dose in TP1 ($ADTM \leq \text{Treatment date/time in the TP1}$). For AOBP, the measurements with the AOBP AOQC=1 will be excluded from baseline determination. If the subject was randomized but has not received the treatment, the Randomization datetime will be used to establish the baseline.

The windowing will be performed by matching the date of the measurement with the date of the visit as reported in the eCRF. For example, if there is a measurement that is obtained on the Week 4 site visit date, that measurement will be used for the Week 4 observation. The measurement for Week 8 will be the one obtained on the Week 8 site visit date as obtained from the raw.sv file and so on. In case there is no measurement that matches the site visit date then the measurement obtained *prior* to the site visit and with the date closest to the site visit date will be used. If there are two competing measurements (e.g. two measurements obtained on the same date), the later measurement on the date will be used.

This procedure will allocate measurements into Study weeks Baseline, Week 2, Week 4, Week 8, Week 10 and Week 12, as applicable. Subjects who do not participate in [REDACTED] may have Week 14/EoS visit. Week 14/EoS visit is Safety Follow-up. Subject is not on the study investigational medications during the Safety Follow-up Period. If there is an EoS Visit Date on the same date of the Study Visit Date, and the subject is on study medications, then the measurement maps into the Study Visit. All measurements that do not map into these visits will be listed but will not contribute to the summaries and analyses.

Next, for the analysis purposes, the measurements need to be organized into the cross-over design pattern, with two baselines corresponding to Study Week 0 and 8 and two treatment visits (Treatment Visit 2 and 4). This is in addition to the above windowing. The ADaM level data set will have data organized both by Study flow (above) and the data organized by Cross-Over design flow.

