This study may use a medication adherence monitoring platform. The platform will be provided on a smartphone application. Built-in reminders and a communication system allow real-time intervention in case of missed doses, reinforce the proper dosing schedule, and improve data integrity.

[REDACTED]

[REDACTED]

[REDACTED]

[REDACTED]

[REDACTED]

If, at any time during the study, a subject experiences a clinically significant laboratory or medical assessment (e.g., hyperkalemia, hyponatremia, symptomatic hypotension, severely elevated BP,

hypercortisolemia, hypocortisolemia, reduction in kidney function), laboratory test results will be confirmed using a local laboratory and AOBP measurements will be repeated. At the discretion of the Investigator, in consultation with the Medical Monitor, the dose of the study drug may be modified, or temporarily or permanently discontinued. The Investigator may temporarily interrupt study drug without prior consultation with the Medical Monitor at their discretion and discuss their decision and whether the interruption should be converted to a discontinuation with the Medical Monitor within 24 hours. A subject with modification of their study drug will not be withdrawn from the study.

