6.4.1.3 Missing Observations for the AOBP SBP

For general guidance about the missing values, see 6.2.7. Guidance on handling the missing observations is provided below.

Table 6 Missing observations imputation for the primary efficacy estimand

Cause for Missing Observation	Type of Missingness	Imputation Approach	Rationale
Lack of follow-up observation in subject with ICE ID #1.	MNAR	Values for the missing observation will be imputed using the distribution for the subjects with ICE ID#1 who do not miss the value (so called “retrieved dropouts”), within the same randomized sequence, if such approach is possible. In case there are not enough retrieved dropouts within the same sequence, the imputation will be performed by Jump to the Reference Group (Placebo Arm)	Retrieved dropouts’ imputation is closest to following a treatment strategy for missing observations. Jump to reference as a last resort is conservative imputation strategy that disfavors treatment effect.
Death for any cause (ICE Event #2)	MNAR	This observation is missing by default. The endpoint will be imputed to assign a poor outcome value by applying a distribution of the worst 5% of the observations across both randomized sequences.	The treatment policy strategy is not applicable as there are no post-event observations. Death, as an unfavorable truncating event prevents observations to be obtained.
Premature study discontinuation in subjects without ICE (e.g. loss to follow-up, withdrawal of consent)	MAR	Values for the missing observations will be imputed using the randomized sequence specific distribution	These observations are assumed to be missing at random and will be imputed as a part of the treatment arm they belong to.

Cause for Missing Observation	Type of Missingness	Imputation Approach	Rationale
Missing observation due to failure to obtain AOBP in subjects without ICE	MAR	Values for the missing observations will be imputed using the randomized sequence specific distribution	AOBP may fail for technical reasons or subject may miss the visit. These observations are assumed to be missing at random and will be imputed as a part of the treatment arm they belong to.

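### SAP 5.5.1 allows a post-dose reading as the TP2 baseline and does not exclude AOQC=1 readings from the Week 4 and Week 12 endpoint values

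*SAP*

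**What the plan says.** SAP 5.5.1 gives the rules for choosing AOBP readings. For the TP1 baseline: "The Study Baseline is the measurement with the datetime of the measurement that is closest to the before the datetime of first dose in TP1". The next sentence is the only mention of AOQC in either document: "For AOBP, the measurements with the AOBP AOQC=1 will be excluded from baseline determination".

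Later visits follow a date-matching rule. For Week 4, "if there is a measurement that is obtained on the Week 4 site visit date, that measurement will be used for the Week 4 observation". For Week 8, "The measurement for Week 8 will be the one obtained on the Week 8 site visit date", and the remaining visits follow the same pattern. For ties: "If there are two competing measurements (e.g. two measurements obtained on the same date), the later measurement on the date will be used". None of these sentences carries a dose-time or AOQC condition.

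SAP 5.5.1 then makes Weeks 0 and 8 the two crossover baselines. SAP 6.4.1.4 brings the Week 8 value into the primary model through xdiff, the difference between the two baselines. SAP 6.2.2 refers the efficacy baseline back to 5.5.1. For non-efficacy crossover endpoints it says that both period baselines are found in the way that 5.5.1 describes.

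**The concern.** A period baseline should be free of that period's treatment. The schedule (Protocol Table 1) places AOBP and in-clinic dosing at the same Week 8 visit. The dose-modification text in Protocol Section 6 foresees repeats after a clinically significant finding: "laboratory test results will be confirmed using a local laboratory and AOBP measurements will be repeated". If a repeat falls on the Week 8 date after dosing, the tie rule selects it. In sequence PL that reading follows the first lorundrostat dose, so any early drug effect would be counted in the baseline.

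Separately, a reading flagged AOQC=1 cannot serve as the Study Baseline, but nothing stops it from serving as the Week 4 or Week 12 value on which the primary test rests. If the flag means what its name suggests, the two ends of the same comparison are held to different validity standards.

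At stake are some bias toward the null from the baseline problem and some added noise from the endpoint problem.

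**Working it through.** The plan states no figure on this point to reproduce. The check is a comparison of the rules, followed by sizing on assumed inputs.

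**Rules side by side (SAP 5.5.1)**

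| AOBP value | How chosen | Pre-dose condition | AOQC=1 excluded |
|---|---|---|---|
| TP1 baseline | closest reading up to first TP1 dose | stated | stated |
| TP2 baseline (Week 8) | visit date, later same-day reading | none stated | ambiguous |
| Week 4 and Week 12 endpoint | visit date, later same-day reading | none stated | not stated |

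Section 5.5.1 also has a rule that picks the assessment closest to the target day. It cannot separate two readings from the same day, so "the later measurement on the date will be used" decides.

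**Shift from a post-dose Week 8 baseline in PL**

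Assumed, because the documents give no rates: a share s = 0.10 of PL subjects is affected, and the affected baseline is too low by a = 5 to 10 mmHg. From SAP 6.1: rho1 is the within-period and rho2 the between-period correlation, with rho2 = rho1 (exchangeable) or rho2 = rho1² (time decay).

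1. Change-score contrast. The treatment effect averages the two sequences' within-subject contrasts, and only PL is affected, so the shift toward the null is s × a / 2. This gives 0.10 × 5 / 2 = 0.25 and 0.10 × 10 / 2 = 0.50 mmHg.
2. Planned xdiff model. The baseline acts only through the slope of the outcome difference on the baseline difference, beta = (rho1 - rho2) / (1 - rho2). The shift is s × a × beta / 2.
   - Exchangeable: rho1 - rho2 = 0, so beta = 0 and the shift is 0.
   - Time decay with rho1 = 0.6: rho2 = 0.36 and beta = 0.24 / 0.64 = 0.375. The shift is 0.10 × 5 × 0.375 / 2 = 0.09 to 0.10 × 10 × 0.375 / 2 = 0.19 mmHg, or 1.7% to 3.4% of the planned 5.5 mmHg.
3. Change-from-baseline summaries (SAP 6.4). The PL mean change in TP2 shifts by s × a = 0.5 to 1.0 mmHg, and the pooled lorundrostat mean by half of that. No model adjustment dampens this.

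As an extreme, suppose every PL subject were affected by 1 to 5 mmHg. The xdiff estimate would shift by 0 under exchangeable correlation and by 0.19 to 0.94 mmHg under time decay. The change-score contrast would shift by 0.5 to 2.5 mmHg.

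**Power loss from flagged endpoint readings**

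The 85% power and 5.5 mmHg are taken from SAP 6.1 as stated. With one-sided alpha 0.05, the implied standard error is 5.5 / (1.036 + 1.645) = 2.05, variance 4.21. If a share f of endpoint readings has extra independent error with standard deviation e, each within-subject difference gains 2 × f × e². The mean over 60 subjects gains 2 × f × e² / 60.

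- f = 0.05, e = 5: gain 0.04, power 84.7%.
- f = 0.10, e = 10: gain 0.33, power 82.5%.
- f = 0.20, e = 15: gain 1.50, power 74.5%.

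Both f and e are assumptions, so the range shows sensitivity and is not a forecast.

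**The case against.** The strongest reply is that much of this may be settled elsewhere. AOQC is undefined. The SAP refers AOBP derivation to a sponsor document, and the protocol refers measurement procedure to the study reference manual and the AOBP site manual. Any of these could remove flagged readings or fix when AOBP is taken relative to dosing. That stands as a caution. However, a separate exclusion at baseline would be redundant if flagged readings had already been removed, and SAP 1.1 calls the SAP the definitive analysis plan.

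Four stronger readings are tempting, and the documents do not support them.

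- A reader might infer that AOQC=1 readings are barred from the TP1 baseline only. The exclusion refers to baseline determination without naming a period, and SAP 6.2.2 suggests one approach for both baselines. The Week 8 date rule does not carry this through, so the position is ambiguous.
- A reader might infer that a post-dose reading at Week 4 or 12 is a fault. It is still on treatment, and nothing requires a pre-dose endpoint.
- A reader might infer that subjects wait in clinic after dosing at Week 8. The 1-2 hour post-dose PK sample is scheduled at Weeks 2, 4, 10 and 12, not Week 8. The repeat-measurement text also does not say that the repeat is on the same day or after the dose.
- A reader might infer that Table 6 of the SAP already handles flagged readings, since it notes that "AOBP may fail for technical reasons or subject may miss the visit". That row covers failure to obtain a reading. It does not say that a recorded but flagged reading counts as missing.

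A later confirmatory reading is also a defensible choice when it is prespecified and blind to treatment. That holds at the endpoint visits, but not where the later reading follows the first dose of the period it is meant to precede.

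**Conclusion.** The point holds as a rule that can select the wrong reading. On the wording of SAP 5.5.1, a reading after the first TP2 dose can become the TP2 baseline, and an AOQC=1 reading can become a primary endpoint value. Handling of AOQC=1 at the TP2 baseline is unclear.

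The expected effect is small. With 10% of PL subjects affected by 5-10 mmHg, the primary estimate moves by 0 under the exchangeable correlation that SAP 6.1 regards as typical, and by about 0.1-0.2 mmHg toward the null under time decay with rho1 = 0.6. Even this range uses a generous assumption, since 5-10 mmHg after one dose is about as large as, or larger than, the 5.5 mmHg planned for four weeks. A reader might infer that the drug effect would be materially understated; the planned model does not support that. The descriptive change-from-baseline summaries are more exposed.

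The power effect rests wholly on assumed flag rates and error sizes, and on the inference that AOQC=1 marks a failed reading. The change is still worth making before unblinding, because it removes a choice that would otherwise fall to programming.

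**What to change.** In SAP 5.5.1:

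1. Define the TP2 baseline as the last valid AOBP reading with a datetime at or before the first TP2 dose, and state that this overrides the later-reading rule at Week 8.
2. Define AOQC. If AOQC=1 marks an invalid reading, exclude it at every AOBP analysis visit (both baselines and Treatment Weeks 2 and 4), so that the later same-day reading is chosen only among valid readings.
3. If no valid reading remains, treat the value as missing under the existing technical-failure row of Table 6.

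No pre-dose requirement is needed for the Week 4 and Week 12 readings.

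The cost is SAP wording and a programming filter. SAP 5.2 already derives the first TP2 administration, and 5.5.1 already compares AOBP and dose datetimes for TP1. The change assumes that a clock time is also held for the first TP2 dose. The downside is that a few flagged readings become missing and are imputed.

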5.5.2 Windowing of vitals and other safety measurements

Vitals will be analyzed according to the nominal visits as reported in the eCRF. They may need to be organized by cross-over design as well or analysis visits (i.e., as reported on the eCRF).

Unscheduled measurements will not be included in by-visit summaries but will contribute to the Baseline timepoint and/or minimum/maximum/worst value (e.g., shift table), if applicable.

Listings will include all visit data, including unscheduled visits, in chronological order based on visit date.

Actual dates and times will be used for pharmacokinetic analyses rather than nominal days and times.

6 STATISTICAL METHODS

6.1 Sample Size Justification

Approximately 60 subjects randomized in a 1:1 ratio to the two sequences (LP and PL) will provide 85% power to detect a placebo-adjusted change in AOBP SBP of at least 5.5 mmHg at Treatment Period Week 4 (pooling both Treatment Periods in a joint longitudinal analysis), assuming 14 mmHg as a standard deviation of change, and 1-sided alpha of 0.05.

Power for a joint analysis is a function of the alternative (assumed 5.5 mmHg), the standard deviation (assumed 14 mmHg), and both the within-treatment-period correlation denoted ρ_1 , and the between-treatment-period correlation denoted ρ_2 . We consider a simple exchangeable correlation model where $\rho_2 = \rho_1$, and a time decay model where $\rho_2 = \rho_1^2$. The following table shows power as a function of the correlation model using analytical expressions for standard errors obtained from the primary linear mixed model analysis:

Correlation (ρ_1)	Power assuming Exchangeable model ($\rho_2 = \rho_1$)	Power assuming Time decay model ($\rho_2 = \rho_1^2$)
0.50	0.819	0.756
0.55	0.850	0.785
0.60	0.882	0.819
0.65	0.915	0.858
0.70	0.945	0.900
0.75	0.971	0.941
0.80	0.988	0.975

Crossover trials generally find a correlation model that closely approximates an exchangeable model since this corresponds to a common magnitude of between subject variation that would be induced from a simple random intercepts model (see Jemielita, Putt and Mehrotra 2016 for examples). Under the exchangeable correlation model, the study has $\geq 85\%$ power provided the correlation is ≥ 0.55 .

6.2 General Statistical Methods

6.2.1 General Methods

Tabulations will be produced for appropriate demographic, baseline, efficacy, pharmacokinetic and safety parameters. For categorical variables, summary tabulations of the number and percentage within each category (with a category for missing data) of the parameter will be presented. For continuous variables, the mean, standard deviation, median, Q1, Q3, minimum and maximum values will be presented. For some parameters with skewed distributions geometric means, geometric standard deviations and geometric confidence intervals will be presented as specified in the Section 6.6.3.3.

Statistical hypothesis testing will be performed for the primary efficacy endpoint, as described in this document. The alpha value used for specific statistical hypothesis is described in Section 6.2.5. Summary statistics will be presented, as well as confidence intervals on selected parameters, as described in the sections below. Statistical testing using nominal p-values will be provided for exploratory endpoints using the alpha value from Section 6.2.5.

Means and medians will be presented with one more decimal place compared to the raw data. Standard deviation will be shown with two more decimal places. Minimum and maximum values will retain the same number of decimal places as in the raw data. Percentages will be displayed with one decimal place.

6.2.2 Definition of Baseline

The baseline for the efficacy measurement is defined in the Section 5.5.1.

Baseline for non-efficacy observations is defined as the last valid assessment on or before the first treatment dosing in TP1 or, for the subjects that are not dosed as the last valid assessment prior to the randomization datetime. If the endpoint refers to the change related to the cross-over design, then the baselines (TP1 and TP2) will be determined in the same fashion as described in the section 5.5.1.

6.2.3 Adjustments for Covariates

No adjustment will be made except as provided in the specific analysis model.

6.2.4 Alpha Value

The overall alpha (α) value is set to one-sided 0.05. The primary and all exploratory endpoints will be tested on the same one-sided alpha of 0.05. The confidence intervals for all analyses will be 90%.

6.2.7 Missing, Unused, and Spurious Data

Unless stated otherwise, missing data will not be replaced with imputed values.

The handling of intercurrent events (ICEs) and sensitivity analyses, including planned handling of missing observations for primary endpoint, are described in Section 6.4.1.2, the rules below will apply unless otherwise specified.

Partial and missing AE or concomitant medication dates will be imputed as described in Section 6.6.

6.3 Study Population

6.3.1 Subject Disposition

Subject disposition will be presented by Randomized Sequence and overall, including the number of subjects screened, screen failed, entered run-in period, completed run-in period and not randomized, randomized, dosed in TP1, dosed in TP2, the number of subjects that withdrew from study treatment and from the study after the randomization in TP1 and TP2 along with the reasons, the number that completed DB Treatment in TP1, TP2 and overall, the number that entered Safety Follow-up Period, and the number that completed the Safety Follow-up Period. The denominator for percentages will be the total number of subjects randomized in each Randomized Sequence, when applicable.

The number of subjects that screen fail at Screening or Randomization and reasons (inclusion/exclusion criteria or other) will be presented by the total number of screen failures.

The following by-subject listings will be presented.

- Study completion information, including the reason for premature study withdrawal, overall and by Treatment period
- Screen failure with inclusion/exclusion criteria
- Randomized patient inclusion in study Analysis Sets or reasons for exclusion.
- Protocol deviations

6.3.2 Demographic and Baseline Characteristics

Demographics and baseline characteristics will be summarized for the total sample. The data will be also listed. The tables will include only Total. The listing will indicate the Randomized Sequence. The characteristics will be presented per baseline definition (e.g. BMI at Baseline).

- Age (years): Age at time of consent
- Age (categories): (< 65, 65-74 and >=75)
- Sex: Male, Female; For women, of childbearing potential, post-menopausal, sterilized

- Race: American Indian or Alaska Native, Asian, Black or African American, Native Hawaiian or Other Pacific Islander, White, Multiple, and Not Reported.
- Ethnicity: Hispanic or Latino, Not Hispanic or Latino, Not reported.
- Height (cm)
- Weight (kg)
- BMI (kg/m²)
- BMI (kg/m²); Categories: (< 30 kg/m² and ≥ 30 kg/m²)
- Hip circumference (cm)
- Waist circumference (cm)
- Waist to Hip Ratio
- Waist to Hip Ratio (WHR): Healthy: < 0.90 [men] and <0.85 [female], Obese: ≥ 0.9 [men] and ≥ 0.85 [women], High Risk: > 1.0 (both men and women).
- AHT regimen (listing only)
- Prescribed AHT regimen (≤2 and 3 or more) as randomized
- AHT Therapy Class (ACT Level)
- SGLT2i status at screening (naïve or not)
- Seated AOBP SBP and DBP (mmHg)
- Seated AOBP SBP Category (<130 mmHg, 130- < 140 mmHg, ≥140 mmHg - <160 mmHg and ≥160 mmHg)
- Standing AOBP SBP and DBP (mmHg)
- Smoking Status (Current, Former, Never)
- History of alcohol abuse (Yes, No)
- History of illicit drug use (Yes, No)
- History of any other tobacco use (Yes, No)
- eGFR (ml/min/1.73m²) (2021 CKD-Epi formula using serum creatinine)
- Baseline eGFR (< 30 mL/min/1.73m², 30-44 mL/min/1.73m², 45-59 mL/min/1.73m², 60-89 mL/min/1.73m², 90 mL/min/1.73m² and more) (2021 CKD-Epi formula using serum creatinine)
- eGFR (ml/min/1.73m²) (2012 CKD-Epi formula using serum Cystatin-C)
- Baseline eGFR (< 30 mL/min/1.73m², 30-44 mL/min/1.73m², 45-59 mL/min/1.73m², 60-89 mL/min/1.73m², 90 mL/min/1.73m² and more) (2012 CKD-Epi formula using serum Cystatin-C)
- UACR (<30 mg/g, 30-<300 mg/g, ≥300 mg/g)

